## 12. Handling of data on tests/timing of assessment

Timing and period category	Handling of data
Time window for efficacy assessment	Before the start of treatment: from the start date of Humira treatment - 30 days to the start date of Humira treatment At Week 4 of treatment: from the start date of Humira treatment + 1 day to the start date of Humira treatment + 42 days At Week 8 of treatment: from the start date of Humira treatment + 43

Timing and period category	Handling of data
	
days to the start date of Humira treatment + 70 days
 
At Week 12 of treatment: from the start date of Humira treatment + 71 days to the start date of Humira treatment + 98 days
 
At Week 16 of treatment: from the start date of Humira treatment + 99 days to the start date of Humira treatment + 140 days
 
At Week 24 of treatment: from the start date of Humira treatment + 141 days to the start date of Humira treatment + 196 days
 
At the final assessment: the data measured at the end during the period from the start date of Humira treatment + 1 day to the start date of Humira treatment + 196 days.

### 13. Diagrams to be created (numbers and names of diagrams)

#### 13.1. General

##### “Figure 1.1 Patient disposition diagram”

Analysis object: Enrolled patients

Purpose of analysis: The number of patients enrolled, number of facilities contracted, number of clinical departments contracted, number of patients with fixed CRFs, number of patients with uncollectible CRFs, number of patients included in the safety analysis set, number of patients excluded from the safety analysis set, number of patients included in the efficacy analysis set, and number of patients excluded from the efficacy analysis set will be calculated. Furthermore, breakdowns of reasons for patients excluded from the safety analysis set and patients excluded from the efficacy analysis set will be calculated.

Note: For a reason for exclusion to which no patient falls under, the entire item should not be output.

##### “Figure 1.2 Breakdown of patients included in the safety analysis set”

Analysis object: Patients included in the efficacy analysis set

Purpose of analysis: For patients included in the safety analysis set, number of patients included in the efficacy analysis set (DAS28-4CRP), number of patients who cannot be assessed with DAS28-4CRP, number of patients included in the efficacy analysis set (CDAI), number of patients who cannot be assessed with CDAI, number of patients included in the efficacy analysis set (SDAI), number of patients who cannot be assessed with SDAI, number of patients included in the efficacy analysis set (DAS28-4/ESR), and number of patients who cannot be assessed with DAS28-4/ESR will be calculated for each efficacy endpoint.

Note: This table will be output on a separate sheet as an appendix to Figure 1.1 Patient composition diagram when the aggregate results in Figure 1.1 is output.

“Table 1.1 Aggregate results of discontinuation of treatment”

Analysis object: Patients included in the safety analysis set

Purpose of analysis: For patients who discontinued treatment and the breakdown of the reasons for discontinuation (remission, subtherapeutic response, onset of adverse events, patient's request, no hospital visit [including hospital transfer], other), the number and percentage of patients will be calculated.

Notes: • The breakdown of the reasons for discontinuation may be redundantly aggregated.

- The denominator of the percentage of patients who discontinued treatment should be patients included in the safety analysis set, and the denominator of the percentage in the breakdown of the reasons for discontinuation should be patients who discontinued treatment as defined in “10.1 General”.
- “Onset of an adverse event” should apply only when “Onset of an adverse event” is selected and an adverse event during safety analysis period has occurred.

“Table 1.2 Aggregate results of switching to other biological products”

Analysis object: Patients included in the safety analysis set

Purpose of analysis: For the number of patients switched to other biological products and the breakdown of the reasons for switching (remission, subtherapeutic response, onset of adverse events, patient's request, no hospital visit [including hospital transfer], other), the number and percentage of patients will be calculated.

Notes: • The breakdown of the reasons for switching may be redundantly aggregated.

- The denominator of the percentage of switched patients should be patients included in the safety analysis set, and the denominator of the percentage in the breakdown of the reasons for switching should be patients switched to other biological products as defined in “10.1 General”.
- “Onset of an adverse event” should apply only when “Onset of an adverse event” is selected and an adverse event during safety analysis period has occurred.

“Table 1.3 Aggregate results of patient background”

Analysis object: Patients included in the safety analysis set, patients included in the efficacy analysis set

Purpose of analysis: The number and percentage of patients by patient background will be calculated.

For quantitative data, basic statistics will also be calculated.

Patient background should follow “11. Data-layer separation” (sex, pregnancy/breastfeeding, age 1, age 2, age 3, body weight, BMI, inpatient/outpatient status at the start of Humira treatment, reason for use and type of disease, disease duration 1, disease duration 2, race, Steinbrocker Staging System, Steinbrocker Functional Classification, administration method category, past medical history, complications, breakdown of complications, history of allergy, breakdown of history of allergy, previous medications, breakdown of previous medications, history of treatment with previous

medications [biological products], breakdown of history of treatment with previous medications [biological products], concomitant drugs, breakdown of concomitant drugs, of the breakdown of concomitant drugs, dose of methotrexate per body surface area, concomitant drug [methotrexate], breakdown of concomitant drug [methotrexate]).

Notes:

- The denominator of the percentage of patients falling under pregnancy/breastfeeding should be “female” (sex) patients.
- The denominators of percentages in items other than the above should be the upper-rank analysis set.
- The reason for use and type of disease, breakdown of complications, breakdown of history of allergy, breakdown of previous medications, breakdown of history of treatment with of previous medications (biological products), breakdown of concomitant drugs, and breakdown of concomitant drug (methotrexate) may be redundantly aggregated.

“Table 1.4 Implementation status of tuberculosis tests (1) (implementation rate of each test)”

Analysis object: Patients included in the safety analysis set

Purpose of analysis: The number and percentage of patients will be calculated for each implementation status (tested, not tested, unknown/unspecified) of tuberculin skin test, Quantiferon test (including T-SPOT), chest x-ray and chest CT before the start of treatment.

Note: None in particular.

“Table 1.5 Implementation status of tuberculosis tests (2) (cross tabulation showing implementation status of tests)”

Analysis object: Patients included in the safety analysis set

Purpose of analysis: The number and percentage of patients will be calculated for each implementation status (no, yes, unknown/unspecified) of immunology test (tuberculin skin test or Quantiferon test or T-SPOT) and imaging procedure (chest x-ray or chest CT) before the start of treatment.

Note: None in particular.

“Table 1.6 Implementation status of prophylactic administration”

Analysis object: Of patients included in the safety analysis set, those who underwent tuberculosis tests.

Purpose of analysis: The number and percentage of patients will be calculated for each result of tuberculosis tests (tuberculin test, tuberculin skin test, Quantiferon test [including T-SPOT]) before the start of treatment by implementation status of prophylactic administration of antituberculosis drugs (no, yes, unknown/unspecified).

Notes:

- Involving patients undergoing tuberculosis tests, cross tabulation should be conducted regarding the tuberculosis test results and prophylactic administration of antituberculosis drugs.

- For the status of prophylactic administration of antituberculosis drugs, data from the registration forms should be used.
- The result categories of each tuberculosis test are shown below.

Tuberculosis test	Tuberculin skin test	Quantiferon test (including T-SPOT)
Positive	Positive	Positive
		Negative
		Not tested
		Indeterminable
		Unknown/unspecified
	Negative	Positive
	Not tested	Positive
	Unknown/unspecified	Positive
Negative	Negative	Negative
	Negative	Unknown/unspecified
	Negative	Not tested
	Not tested	Negative
	Unknown/unspecified	Negative
Indeterminable	Negative	Indeterminable
	Not tested	Indeterminable
	Unknown/unspecified	Indeterminable
Unknown	Unknown/unspecified	Negative
	Negative	Unknown/unspecified
	Not tested	Unknown/unspecified
	Unknown/unspecified	Not tested

“Table 1.7 Implementation status of hepatitis B tests”

Analysis object: Patients included in the safety analysis set

Purpose of analysis: The number and percentage of patients will be calculated for each implementation status (tested, not tested, unknown/unspecified) of hepatitis B test (HBs antigen test, HBs antibody test, HBc antibody test). Where tests were performed, the number and percentage of patients will also be calculated for breakdown of their results (negative, positive, unknown/unspecified).

Note: None in particular.

“Table 1.8 Status of Humira treatment (dosage and administration)”

Analysis object: Patients included in the safety analysis set

Purpose of analysis: For the status of Humira treatment (dosage and administration) (20 mg/2 weeks, 40 mg/2 weeks, 20 mg/2 weeks → 40 mg/2 weeks, other), the number and percentage of patients will be calculated.

Note: Patients who received doses other than “20 mg/2 weeks”, “40 mg/2 weeks”, “20 mg/2 weeks

→ 40 mg/2 weeks” should be categorized into “other”.

“Table 1.9 Status of Humira treatment (number of doses, days to the date of the last dosing)”

Analysis object: Patients included in the safety analysis set

Purpose of analysis: For the status of Humira treatment (number of doses, days to the date of the last dosing), the number and percentage of patients will be calculated by category defined in “11. Data-layer separation”.

Note: Where the last record of the treatment status is checked for “ongoing” or where the end date of treatment exceeds the start date of treatment + 168 days, the end date of treatment should be handled as the start date of treatment + 168 days.

“Table 1.10 Dose by body weight at the start of treatment”

Analysis object: Patients included in the safety analysis set

Purpose of analysis: The number and percentage of patients will be calculated for each category of dose at the start of Humira treatment as defined in “11. Data-layer separation” (number of doses, days to the date of the last dosing) by body weight at the start of Humira treatment (<15 kg, ≥15 kg and <30 kg, ≥30 kg, unknown/unspecified).

Note: The denominator of the percentage of the number of patients should be patients included in the safety analysis set.

“Table 1.11 Incidence rate of administration errors caused by self-injection”

Analysis object: Patients included in the safety analysis set

Purpose of analysis: The number and percentage of patients will be aggregated by the status of self-administration (no, yes, unknown/undescribed). Where self-administration was conducted, the number and percentage of patients will be calculated for each category of errors caused by self-administration defined in “11. Data-layer separation” (self-administration, errors caused by self-administration).

Notes: The denominator of the percentage of errors caused by self-administration should be patients who conducted self-administration (“yes”).

“Table 1.11.1 Incidence rate of administration errors caused by self-injection (by age)”

Analysis object: Patients included in the safety analysis set

Purpose of analysis: The number and percentage of patients will be calculated for “11. Data-layer separation” (age category 3) by the status of self-administration (no, yes, unknown/undescribed).

Where self-administration was conducted, the number and percentage of patients will be calculated for each age category (age category 3) by category of errors caused by self-administration defined in “11. Data-layer separation” (self-administration, errors caused by self-administration).

Notes: The denominator of the percentage of errors caused by self-administration should be patients

who conducted self-administration (“yes”).

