Footnotes	
Where it is considered necessary to provide an explanation in association with preparation of analysis results, provide the explanation in a footnote.
 
Footnotes should be in the following form:
 
Add a superscript “*sequential number” on the right side of a term, etc. that you want to explain, and provide the “*sequential number” corresponding to the footnote and the explanation under the diagram.

Percentage	
When a percentage is calculated, the denominator should be the number of patients in the analysis set.
 
*Specify in a footnote when the denominator used for calculation of a percentage in the same table is different from the number of patients in the analysis set.
 
When percentages for a breakdown of a factor or item are calculated, ensure that the total becomes 100%. Any item redundantly counted should be specified in a footnote.

Context of numbers	When a figure such as a patient composition figure is created, all numbers required to maintain consistency of the context of numbers should be provided.

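### SAP Table 1.6 lists two tuberculosis test combinations under both Negative and Unknown, so the plan does not determine the counts in those two rows

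*SAP*

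**What the plan says.** The analysis object of SAP Table 1.6 (section 13.1) is "Of patients included in the safety analysis set, those who underwent tuberculosis tests". The notes to the table say that "cross tabulation should be conducted regarding the tuberculosis test results and prophylactic administration of antituberculosis drugs". The overall result has four values (Positive, Negative, Indeterminable, Unknown), and each is defined by a list of skin-test and Quantiferon/T-SPOT pairs, introduced by "The result categories of each tuberculosis test are shown below".

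The second row of the Negative block gives the pair "Negative Unknown/unspecified" (skin test first, then Quantiferon). The same pair is the second row of the Unknown block. The first row of the Unknown block reads "Unknown Unknown/unspecified Negative": overall result Unknown, skin test unknown/unspecified, Quantiferon negative. That pair is also the fifth row of the Negative block.

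SAP section 9.10 sets two general rules on percentages. The first is "When percentages for a breakdown of a factor or item are calculated, ensure that the total becomes 100" per cent. The second is "Any item redundantly counted should be specified in a footnote".

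**The concern.** A derived category should send each patient to exactly one row, unless the plan says that multiple counting is intended. Here two pairs have two destinations. Two programmers working from this SAP could produce different Negative and Unknown rows, and each could claim to have followed it.

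Table 1.6 is the table that sets the screening result against prophylaxis, and SAP section 3.1 says that the analyses serve reporting to the authorities and the reexamination application. What is at stake is how many patients are reported as test-negative, how many as unknown, and the share in each row who received prophylaxis.

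**Working it through.** **Inputs.** All come from the Table 1.6 mapping and SAP section 9.10. There is no planned figure to reproduce.

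**Step 1: count the rows.** Positive has 8, Negative 5, Indeterminable 3 and Unknown 4. In the Positive block, blank skin-test cells are read as carrying the value above. Total: 8 + 5 + 3 + 4 = 20 rows.

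**Step 2: set the two blocks side by side.**

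| Skin test | Quantiferon/T-SPOT | Listed under Negative | Listed under Unknown |
|---|---|---|---|
| negative | negative | yes | no |
| negative | not tested | yes | no |
| not tested | negative | yes | no |
| negative | unknown/unspecified | **yes** | **yes** |
| unknown/unspecified | negative | **yes** | **yes** |
| not tested | unknown/unspecified | no | yes |
| unknown/unspecified | not tested | no | yes |

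Two pairs are duplicated. The Positive and Indeterminable blocks share no pair with any other block. So 20 rows hold 20 − 2 = 18 distinct pairs.

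**Step 3: check coverage.** Four skin-test values (positive, negative, not tested, unknown/unspecified) and five Quantiferon values (the same plus indeterminable) give 4 × 5 = 20 possible pairs. With 18 mapped, 20 − 18 = 2 have no row: not tested with not tested, which lies outside the table's population, and unknown with unknown, which is discussed under the objection.

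**Step 4: effect on the counts.** Let n be the number of tested patients, k the number in the two shared cells, a the number in the three pairs listed only under Negative, and b the number in the two pairs listed only under Unknown. Suppose every patient has at least one row.

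- Literal application: Negative = a + k and Unknown = b + k. The rows sum to n + k, or 100(n + k)/n per cent. The excess is 100k/n percentage points.
- Single assignment by the programmer: the total is 100 per cent, but Negative can lie anywhere from a to a + k and Unknown from b + k to b, depending on the choice made for each pair.

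Neither n nor k is in the documents. At k = 0 the total is 100 per cent and nothing changes. If n were 100 (an assumption, taking the target sample size as the number tested), each affected patient would add 100 × 1/100 = 1 percentage point under literal application.

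**Step 5: look for a rule elsewhere.** SAP section 10.1 names only the source fields for the two tests. Section 11 gives implementation categories for each test, not a combined result. Section 9.3 keeps unknowns in denominators but does not say which row they belong to. Tables 1.1, 1.2 and 1.3 carry notes that allow a patient to be counted more than once; Table 1.6 carries none.

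**The case against.** **No one need be double counted.** Section 9.10 requires a breakdown to total 100 per cent, and Table 1.6 has no note permitting repeated counting. Read together, these point to one row per patient. That stands. A reader might infer from the duplicated pairs that patients will be counted twice; the documents support this only if the mapping is applied literally. What remains is that, under single assignment, nothing says which row.

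**The table carries little weight.** This also stands. A reader might infer that the tuberculosis safety results are affected, because tuberculosis is an item of particular interest in Protocol section 1. That item concerns the occurrence of the disease, reported in SAP Table 2.4, which does not use this mapping. The combined result is not a factor in Tables 2.5.1, 3.1 or 3.5.2, and no test or confidence interval depends on it. Tables 1.4 and 1.5 report the implementation of the tests separately, and Table 4.2 lists the individual tests by patient.

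**Unknown with unknown may not be a gap.** Section 11 treats unknown/unspecified as an alternative to tested, so a patient with both unknown may not count as having been tested. On the other side, the Unknown block includes pairs of not tested with unknown, where no result is known either. The plan is unclear here; the documents do not establish an omission.

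**The overlap might be damage from PDF extraction.** This is unlikely. Blank cells occur only in the Positive block, and every row of the Negative and Unknown blocks shows both test results.

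**Conclusion.** The inconsistency is real and narrow. Two of the 18 distinct pairs have two destinations and no rule to choose between them. The Negative and Unknown counts are therefore undetermined by up to k patients each, as are the prophylaxis percentages in those rows. Literal use also breaks the SAP's own 100 per cent rule whenever k is above 0. The size in practice is unknown and may be nil.

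A reader might also infer that the two pairs must belong under Unknown, because one test is unknown. The mapping does not support that. Elsewhere a known result decides when the other is unknown or not tested: unknown with positive is Positive, unknown with indeterminable is Indeterminable, and negative with not tested is Negative. Placing the pairs under Negative fits that pattern better, though the documents do not settle the choice.

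Severity is low: this is a clarification to one descriptive screening table. The conclusion rests on reading the mapping rows as printed.

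**What to change.** List each of the two pairs once. The option consistent with the rest of the mapping is to keep both under Negative and delete them from Unknown. If the sponsor prefers Unknown, delete them from Negative instead. Either way 18 rows then cover 18 distinct pairs, each in one category.

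Also state whether patients with both results unknown/unspecified belong to the table's population. If they do, add that pair to Unknown, which gives 18 + 1 = 19 rows and leaves only not tested with not tested, outside the population.

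The cost is two deleted rows, possibly one added row, and one sentence. No new data are needed, and no patient's testing or treatment is affected.

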### 13.2. Safety

#### “Table 2.1 Appended Form 2”

Analysis object: Patients included in the safety analysis set

Purpose of analysis: Involving adverse events during the safety analysis period, the following items will be aggregated by period.

Number of investigating facilities: Number of facilities included in the survey.

When multiple clinical departments in a single facility have been contracted, they should be counted as one facility.

Number of patients surveyed: Number of patients included in the safety analysis set.

Number of patients who experienced adverse reactions, etc.: Number of patients who experienced adverse reactions.

Number of adverse reactions, etc.: Number of adverse reactions that occurred.

When a single patient experienced multiple episodes of the same adverse reaction (PT), they should be counted as one event.

Percentage of patients who experienced adverse reactions, etc. (%): Number of patients who experienced adverse reactions, etc. ÷ number of patients included in the safety analysis set x 100.

Types of adverse reactions, etc.: Should be calculated by SOC and by PT.

Output data should be sorted in the order of international agreements and in the ascending PT code order. When a single patient experienced multiple episodes of the same adverse reaction (PT), they should be counted as one event.

Notes: • The categories of period should be status up to approval, special drug use-results survey, and total.  
• The version of MedDRA/J used should be provided.  
• Adverse reactions and infections that cannot be expected from “Precautions” in the package insert should be indicated with \*.

#### “Table 2.2 Appended Form 10”

Analysis object: Patients included in the safety analysis set

Purpose of analysis: Involving adverse events during the safety analysis period, the following items will be aggregated by period.

Number of investigating facilities: Number of facilities included in the survey.

When multiple clinical departments in a single facility have been contracted, they should be counted as one facility.

Number of patients surveyed: Number of patients included in the safety analysis set.

Number of patients who experienced events: Number of patients who

experienced serious adverse events.

Number of cases: Number of serious adverse events that occurred. When a single patient experienced multiple episodes of the same serious adverse event (PT), they should be counted as one event.

Percentage of patients who experienced events: Number of patients who experienced serious adverse events ÷ number of patients included in the safety analysis set x 100.

Types of serious adverse events: Should be calculated by SOC and by PT. Output data should be sorted in the order of international agreements and in the ascending PT code order. When a single patient experienced multiple episodes of the same serious adverse event (PT), they should be counted as one event.

Notes:

- The categories of period should be status up to approval, drug use-results survey, special drug use-results survey, post-marketing clinical study, and total.
- The version of MedDRA/J used should be provided.
- Adverse events that cannot be expected from “Precautions” in the package insert should be indicated with \*.
- The number of events for which the causal relationship was ruled out should be shown in [ ].

“Table 2.3 List of incidence of adverse reactions in this survey”

Analysis object: Patients included in the safety analysis set

Purpose of analysis: Adverse reactions or serious adverse reactions during the safety analysis period will be aggregated as follows.

Number of patients surveyed: Number of patients included in the safety analysis set.

Number of patients who experienced adverse reactions (or serious adverse reactions): Number of patients who experienced adverse reactions (or serious adverse reactions).

Number of adverse reactions (or serious adverse reactions): Number of adverse reactions (or serious adverse reactions) that occurred. When a single patient experienced multiple episodes of the same adverse reaction (PT), they should be counted as one event.

Percentage of patients who experienced adverse reactions (or serious adverse reactions): Number of patients who experienced adverse reactions (or serious adverse reactions) ÷ number of patients included in the safety analysis set x 100.

Types of adverse reactions (serious adverse reactions): Should be calculated by SOC and by PT. Output data should be sorted in the order of international agreements and in the ascending PT code order. When a single patient experienced multiple episodes of the same adverse reaction (PT), they should

be counted as one event.

Note: The version of MedDRA/J used should be provided.

“Table 2.4 List of incidence of adverse events and adverse reactions by priority survey item”

Analysis object: Patients included in the safety analysis set

Purpose of analysis: For adverse events during the safety analysis period or adverse reactions during the safety analysis period, the number and percentage of patients will be calculated for each priority survey item (infection, tuberculosis, interstitial pneumonia, malignant tumour, congestive cardiac failure, autoimmune disease, pancytopenia, demyelinating disease, administration site reaction) by seriousness (non-serious, serious, overall).

Note: None in particular.

“Table 2.5.1 Incidence of adverse reactions by patient background factor”

Analysis object: Patients included in the safety analysis set

Purpose of analysis: Involving adverse reactions during the safety analysis period, the number of patients and the number and percentage of patients who experienced adverse reactions will be calculated in accordance with “11. Data-layer separation” (age 1, age 2, age 3, sex, body weight, BMI, reason for use and type of disease, disease duration 2, complications, complication: liver disorder, complication: renal disorder, complication: cardiovascular disorder, complication: blood disorder, complication: respiratory disorder, complication: other, past medical history, history of allergy, Steinbrocker Staging System, Steinbrocker Functional Classification, administration method category, previous medications, status of previous medication: biological product, status of previous medication: MTX, status of previous medication: corticosteroid, status of previous medication: NSAIDs, status of previous medication: Other DMARDs, concomitant drugs, status of concomitant drug: MTX, status of MTX: details, status of concomitant drug: corticosteroid, status of concomitant drug: NSAIDs, status of concomitant drug: Other DMARDs).

For the incidence rates of adverse reactions, Fisher's exact test should be conducted when the background factor is a nominal scale and Mann-Whitney U test should be conducted when the background factor is an ordinal scale.

Notes: • Reason for use and type of disease may be redundantly aggregated. No test will be conducted for this item.

“Table 2.5.2 Incidence of adverse events in patients switched to other biological products”

Analysis object: Patients included in the safety analysis set

Purpose of analysis: Involving adverse events during the safety analysis period, the number of patients, the number and percentage of patients who experienced adverse events will be calculated on the basis of the number of patients switched to

other biological products and the breakdown of the reasons for switching (remission, subtherapeutic response, onset of adverse events, patient's request, no hospital visit [including hospital transfer], other).

Notes:

- The breakdown of the reasons for switching may be redundantly aggregated.
- “Onset of an adverse event” should apply only when “Onset of an adverse event” is selected and an adverse event during safety analysis period has occurred.

“Table 2.5.3 Incidence of adverse reactions to combination therapy for juvenile idiopathic arthritis”

Analysis object: Patients included in the safety analysis set

Purpose of analysis: Involving adverse reactions during the safety analysis period, the number of patients, the number and the percentage of patients who experienced adverse reactions will be calculated on the basis of combination therapy for juvenile idiopathic arthritis (no, yes, unknown/unspecified). For patients receiving combination therapy, the number of patients, the number and percentage of patients who experienced adverse reactions by breakdown of combination therapy (rehabilitation, other, unknown/unspecified) will be calculated.

Notes: The breakdown of combination therapy may be redundantly aggregated.

“Table 2.5.4 Incidence of adverse reactions by duration of combination use of MTX for juvenile idiopathic arthritis”

Analysis object: Patients included in the safety analysis set

Purpose of analysis: Involving adverse reactions during the safety analysis period, the number of patients, the number and the percentage of patients who experienced adverse reactions will be calculated on the basis of duration of combination use of MTX for juvenile idiopathic arthritis (no, yes, unknown/unspecified). Where there is a duration of combination use of MTX, the number of patients, the number and percentage of patients who experienced adverse reactions by breakdown of duration of combination use (after the start of Humira treatment up to the end date of Humira treatment, at least a dose used during Humira treatment, unknown/unspecified) will be calculated.

Notes: The breakdown of duration of combination use may be redundantly aggregated.

“Table 2.5.5.X Examination of factors affecting the occurrence of adverse reactions”

Analysis object: Patients included in the safety analysis set

Purpose of analysis: For factors with a significant difference ( $p < 0.05$ ) in “Table 2.5.1”, adverse reactions during the safety analysis period will be aggregated by stratification factor as shown below. The number of patients analyzed, the number and percentage of patients who experienced adverse reactions, the number of adverse reactions, the number of patients who experienced adverse reactions by type of adverse reaction (by SOC and PT) and their percentages against the patients analyzed will be calculated.

Number of patients who experienced adverse reactions (or serious adverse

reactions): Number of patients who experienced adverse reactions (or serious adverse reactions).

Number of adverse reactions (or serious adverse reactions): Number of adverse reactions (or serious adverse reactions) that occurred. When a single patient experienced multiple episodes of the same adverse reaction (PT), they should be counted as one event.

Types of adverse reactions (serious adverse reactions): Should be calculated by SOC and by PT. Output data should be sorted in the order of international agreements and in the ascending PT code order. When a single patient experienced multiple episodes of the same adverse reaction (PT), they should be counted as one event.

Note: • A form should be created for each factor.  
• The version of MedDRA/J used should be provided.

“Table 2.6 Incidence of adverse reactions by disease type category”

Analysis object: Patients included in the safety analysis set

Purpose of analysis: Adverse reactions during the safety analysis period will be aggregated in accordance with “11. Data-layer separation” (reason for use and type of disease) as shown below. The number of patients analyzed, the number and percentage of patients who experienced adverse reactions, the number of adverse reactions, the number of patients who experienced adverse reactions by type of adverse reaction (by SOC and PT) and their percentages against the patients analyzed will be calculated.

Number of patients who experienced adverse reactions (or serious adverse reactions): Number of patients who experienced adverse reactions (or serious adverse reactions).

Number of adverse reactions (or serious adverse reactions): Number of adverse reactions (or serious adverse reactions) that occurred. When a single patient experienced multiple episodes of the same adverse reaction (PT), they should be counted as one event.

Types of adverse reactions (serious adverse reactions): Should be calculated by SOC and by PT. Output data should be sorted in the order of international agreements and in the ascending PT code order. When a single patient experienced multiple episodes of the same adverse reaction (PT), they should be counted as one event.

Note: The version of MedDRA/J used should be provided.

“Table 2.7 Incidence of adverse reactions by body weight”

Analysis object: Patients included in the safety analysis set

Purpose of analysis: Adverse reactions during the safety analysis period will be aggregated in accordance with “11. Data-layer separation” (body weight) as shown below. The number of patients analyzed, the number and percentage of patients who

experienced adverse reactions, the number of adverse reactions, the number of patients who experienced adverse reactions by type of adverse reaction (by SOC and PT) and their percentages against the patients analyzed will be calculated.

Number of patients who experienced adverse reactions: Number of patients who experienced adverse reactions.

Number of adverse reactions: Number of adverse reactions that occurred. When a single patient experienced multiple episodes of the same adverse reaction (PT), they should be counted as one event.

Types of adverse reactions: Should be calculated by SOC and by PT. Output data should be sorted in the order of international agreements and in the ascending PT code order. When a single patient experienced multiple episodes of the same adverse reaction (PT), they should be counted as one event.

Note: The version of MedDRA/J used should be provided.

